## 9.3.3 Interim Analysis

There are no planned interim analyses.

## 10.0 STUDY MANAGEMENT

## **10.1 Conflict of Interest**

Any reportable conflict of interest will be disclosed to the local IRB and will be outlined in the Informed Consent Form.

## 10.2 Institutional Review Board (IRB) Approval and Consent

It is expected that the IRB will have the proper representation and function in accordance with federally mandated regulations. The IRB should approve the consent form and protocol.

In obtaining and documenting informed consent, the investigator should comply with the applicable regulatory requirement(s), and should adhere to Good Clinical Practice (GCP) and to ethical principles that have their origin in the Declaration of Helsinki.

Before recruitment and enrollment onto this study, the patient will be given a full explanation of the study and will be given the opportunity to review the consent form. Each consent form must include all the relevant elements currently required by the FDA Regulations and local or state regulations. Once this essential information has been provided to the patient and the investigator is assured that the patient understands the implications of participating in the study, the patient will be asked to give consent to participate in the study by signing an IRB-approved consent form.

Prior to a patient's participation in the trial, the written informed consent form should be signed and personally dated by the patient and by the person who conducted the informed consent discussion.

#### **10.3 Registration Procedures**

All subjects that sign informed consent will be assigned a screening identification number by the study coordinator sequentially by their date of consent, please refer to MOP. Those subjects that do not pass the screening phase will be listed as screen failures on the master list of consented subjects. Eligible subjects, as determined by screening procedures and verified by a treating investigator, will be registered on study by the Study Coordinator.

Issues that would cause treatment delays after registration should be discussed with the site PI and CSMC protocol PI. If a patient does not receive protocol therapy following registration, the patient's registration on the study may be canceled. The Study Coordinator should be notified of cancellations as soon as possible.

The study team will track all subjects who sign consent on a subject screening/enrollment log using a unique screening ID. Subjects found to be ineligible will be recorded as screen failures. Subjects found to be eligible will be registered.

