# Pre-Screen Chart Review – Initial determination of eligibility (N=162; 33 at CSMC, 32 at UCLA, 32 at NWU, 32 at UCSF, and 32 at EU)

Medical charts of patients with HCC reviewed for cirrhosis diagnosis, prior or current statin use, prohibited concomitant medications, medical contraindications, laboratory results, size and number of tumors from staging scan (confirm meeting Milan Criteria or OPTN tumor downstaging criteria), first liver directed therapy followed by an MRI or CT to verify HCC response. A study information packet that includes an introductory letter, leaflet, consent and HIPAA forms will be mailed to potentially eligible patients. Study coordinator will call all potentially eligible patients to introduce the study and answer questions.

Screening Visit – Consent and Final determination of eligibility (N=144; 29 at CSMC, 28 at UCLA, 28 at NWU, 28

at UCSF, and 28 at EU)

Patients who are eligible based on pre-screen chart review will be consented into the trial before any research procedures are initiated. Study physician will thoroughly review the patient's medical history and medications and evaluate all inclusion/exclusion criteria. Patients will undergo blood tests to confirm eligibility and safety of statin initiation; urine pregnancy test for women able to become pregnant. Patients with a MELD score  $\geq 30$  or, AST/ALT > 5x ULN; and women who are pregnant will be excluded.

**Eligible, consented patients with HCC randomized to pravastatin or placebo (N=130; 26 per site)** Pravastatin 40 mg, daily for 12 months Placebo identical in color, consistency, and appearance to

statin 40 mg, daily for 12 months	Placebo identical in color, consistency, and appearance
(N=65)	pravastatin 40 mg, daily for 12 months (N=65)

Study Visit 1 – Baseline / initiation of intervention (0-30 days following Screening Visit)

Review medical history, medications, and laboratory test results; symptom assessment; ECOG performance status; blood draw; MRE with fat fraction or FibroScan for liver stiffness testing review inclusion/exclusion criteria; interviewer-administered questionnaire; dispense study drug and diary

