## STUDY SUMMARY

Title	Pravastatin Intervention to Delay Hepatocellular Carcinoma Recurrence
Protocol Number	IIT2017-[name]-StatLv
Phase	Phase II
Methodology	Randomized, double-blinded, placebo-controlled, Phase II trial of statin to increase time to recurrence in patients with liver cirrhosis and initial hepatocellular carcinoma
Study Duration	5 years
Study Center(s)	Cedars-Sinai Medical Center (CSMC), Ronald Reagan UCLA Medical Center (UCLA), Northwestern Memorial Hospital (NWU), UCSF Medical Center (UCSF), Emory University Woodruff Health Sciences Center (EU)
	Primary Objective: To evaluate the effect of a pravastatin intervention versus placebo on the change in time to recurrence (TTR) from baseline to 12 months following treatment initiation.
Objectives	
 
Secondary Objective: To evaluate the effect of a pravastatin intervention versus placebo at 12 months from baseline on:
 
1) Recurrence-free survival
 
2) Overall survival
 
3) Waitlist drop-off
 
4) Change in liver stiffness
 
5) Change in liver fat fraction
 
6) Change in serum biomarkers of monocyte/macrophage and stellate cell activation
 
7) Levels of liver tissue markers related to HCC
 

Number of Subjects	130
Diagnosis and Main Inclusion Criteria	Patients with a confirmed diagnosis of liver cirrhosis (Child-Pugh A or B); current Model for End-Stage Liver Disease (MELD) < 30; Minimum 18 years of age; HCCs must fall within the Milan Criteria or OPTN tumor downstaging criteria; receipt of LRT with verification of adequate response; and patients whose lab results meet the inclusion criteria after the Screening visit blood tests.
Study Product(s), Dose, Route, Regimen	Pravastatin 40 mg and placebo identical in color, consistency, and appearance to pravastatin; oral administration daily (N=65 in each group)
Duration of administration	12 months
Statistical Methodology	Statistical analyses for the primary objective will be conducted on participants who complete the 12 month MRI or CT and blood specimen collection. The distribution of the clinical and demographical covariates, including but not limited to; age, race, smoking status, BMI, and comorbid conditions, will be summarized and compared between the intervention and control groups to assess the adequacy of the randomization. Chance differences between groups will be adjusted for using multiple regression modeling.

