## • Primary Efficacy Endpoint

Following the American Association for the Study of Liver Diseases-Journal of the National Cancer Institute guidelines for trial design in HCC, we have set our primary endpoint as TTR, according to the recommendation for Phase II studies that assess adjuvant therapies secondary to liver directed therapy (33). TTR will be defined as the time from randomization to the first occurrence of a documented HCC recurrence or HCC death, within the 12-month intervention and assessment period. Participants who experience death attributed to their underlying liver cirrhosis, or other cause, will be censored at death date. For participants who do not recur or die and are lost to follow-up prior to the 12-month study visit, analysis of TTR will be censored at their last date of evaluable scan before drop-out.

In this study, we will rely heavily on the mRECIST outcome guidelines and the Liver Imaging Reporting and Data System (LI-RADS) diagnostic algorithm for defining hepatic recurrence (34, 35), and central expert independent radiographic review by MedQIA.

Pathological Definition: Participants who receive a transplant will become ineligible at the time of transplantation. Recurrent HCCs may also be identified at time of transplantation during the examination of the explant by a pathologist. These "incidental" HCCs represent a sizable proportion, amounting to 22% of HCCs among those receiving a liver transplant. Thus, if transplantation occurs and a pathologically confirmed HCC is detected, we will examine these pathologically defined tumors as a **secondary** definition of recurrence.

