#### 5.3 Blinding/Unblinding

Due to the objectives of the study, the identity of test and control treatments will not be known to investigators, research staff, or subjects. The following study procedures will be in place to ensure double-blind administration of study treatments.

- The study biostatisticians will set up randomization blocks.
- After registration, participants will be randomized to treatment with the study agent or placebo
- Investigators and participants will be blinded as to the result of randomization. The following people will be unblinded: the study biostatisticians at Cedars-Sinai and the investigational pharmacists at each participating site.
- The investigational pharmacist will manage the study agent and placebo.
- Unblinding will only occur when it is deemed medically necessary.

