# 6.1.1 Screening Visit- Consent, Final determination of eligibility, registration, and randomization

After consent has been obtained, a final assessment of eligibility will be conducted. Consented patients will undergo additional screening and testing at the clinic to confirm eligibility and safety of study drug initiation.

For definition of any procedures, please see section 3.1 Study Measurements. The following procedures will be performed during the Screening Visit:

- Physical assessment
- Pregnancy test
- Imaging review
- Eligibility blood specimen
  - o AFP
  - o Blood chemistry
  - PT/INR
- Review Subject Eligibility Criteria

• All inclusion and exclusion criteria will be evaluated for the patient

- Registration and randomization
  - Eligible participants will be registered and randomized to pravastatin or placebo

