#### 6.2.2 Study Visit 1- Baseline Testing and Initiation of the Intervention

Study Visit 1 (Baseline measurements) will occur 0-30 days after the Screening Visit. The following procedures will be performed during this visit:

- Medical history
- Concomitant medication review
- Health assessment
- Clinical blood specimen
  - Blood chemistry
    - o Lipid
    - HbA1C
  - CPK
  - Research blood specimen
- Liver stiffness
- Liver fat fraction
- Baseline risk factor questionnaire

- Baseline symptom assessment
- Study agent
  - Dispense the study agent (one bottle of 120 capsules) and review instructions for how to take it
  - Dispense and review the study diary

## 6.2.3 Study Visit 2

Study Visit 2 will occur 1 month (± 15 days) after initiation of the Intervention. The following procedures will be performed during this visit:

- Symptom/adverse events assessment
- Medical history
- Concomitant medications review
- Health assessment
- Clinical blood specimen
  - Blood chemistry
  - o Lipid
- Imaging review
- Study agent
  - Collect study agent and diary
  - Assess compliance (pill count)
  - Review study diary
  - Dispense study agent (same bottle that was brought to the visit/collected for pill count)

## 6.2.4 Study Visit 3

Study Visit 3 will occur 3 months ( $\pm$  15 days) after initiation of the intervention (study drug initiation).

The following procedures will be performed during this visit:

- Symptom/adverse events assessment
- Medical history
- Concomitant medications review
- Health assessment
- Imaging review
- Study agent
  - Collect study agent and diary
  - Assess compliance (pill count)
  - Review study diary
  - o Dispense study agent (one new bottle of 120 capsules) and diary

## 6.2.5 Study Visit 4

Study Visit 4 will occur 6 months ( $\pm$  15 days) after initiation of the Intervention (study drug initiation). The following procedures will be performed during this visit:

- Symptom/adverse events assessment
- Medical history
- Concomitant medications review
- Physical assessment
- Clinical blood specimen
  - Blood chemistry
  - o Hba1c
  - $\circ$  AFP
- Research blood specimen
- Follow-up risk factor questionnaire

- Imaging review
- Study agent
  - Collect study agent and diary
  - Assess compliance (pill count)
  - Review study diary
  - Dispense study agent (one bottle of 120 capsules) and diary

## 6.2.6 Study Visit 5

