#### 10.3.2 Randomization

After eligibility is verified, study coordinator assigns the participant ID (PID) and registration is completed as follows:

- The study coordinator at each site will send an email to the research pharmacist.
- Site investigational pharmacist enters patient data into RANDI3 software (housed on CSMC server) for randomization, and assigns patient to pravastatin or placebo, and emails the study coordinator that randomization has been completed.

• Study coordinator enters the patient in OnCore to complete registration Only the research pharmacists and the study biostatistician are unblinded; all other study team members are blinded and should not have access to the subject's treatment arm. See Pharmacy Manual for more details.

Research pharmacists can only view subjects they have randomized at their site. The study biostatistician maintains the master randomization list and is responsible for the predetermined randomization scheme prior to the start of study. Of note, the inform and participant eligibility form must be completed prior to randomization

Oversight by the site PI and CSMC protocol PI are required throughout the entire registration process.

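### A randomised patient who never starts study drug can have the registration cancelled, and no rule keeps that patient in follow-up or analysis

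*Combined protocol and SAP*

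**What the plan says.** **Allocation.** Section 6.1.1 lists this among the Screening Visit procedures: "Eligible participants will be registered and randomized to pravastatin or placebo". The schedule of events also marks registration and randomisation in the screening column only.

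**Order of steps.** In Section 10.3.2 the site pharmacist first allocates the patient in RANDI3, and then "Study coordinator enters the patient in OnCore to complete registration". Section 5.3 gives the reverse order: "After registration, participants will be randomized to treatment with the study agent or placebo".

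**First dose.** Section 6.2.2 says: "Study Visit 1 (Baseline measurements) will occur 0-30 days after the Screening Visit". Study drug is first dispensed at that visit.

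**Cancellation.** Section 10.3 says: "If a patient does not receive protocol therapy following registration, the patient's registration on the study may be canceled". The sentence before it concerns delays to treatment after registration, so the protocol foresees a gap.

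**Endpoint clock.** Section 2.3 says: "TTR will be defined as the time from randomization to the first occurrence of a documented HCC recurrence or HCC death". RFS and OS are also timed from randomisation.

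**Who is followed and analysed.** Section 6.6 continues endpoint follow-up, if possible, for participants who stop the agent. Section 5.11 rules out replacing those who withdraw from treatment and is silent on cancelled registrations. The Study Summary says: "Statistical analyses for the primary objective will be conducted on participants who complete the 12 month MRI or CT and blood specimen collection". No intention-to-treat set is defined.

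**The concern.** Once a patient has been allocated, whether the patient later takes the drug is a post-randomisation fact. A rule that lets such a patient drop off the trial's books because no dose was taken permits post-randomisation exclusion. Here it sits beside endpoints whose clock has already started. A death between allocation and Visit 1 is an OS event, and a TTR event if it is due to HCC; a documented recurrence is a TTR and RFS event. Yet these are among the reasons why a patient might never start the drug. At stake are the integrity of the randomised comparison, the completeness of the event count, and the consistency of site practice, because the two stated orders of registration and randomisation leave it unclear what a cancelled patient is.

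**Working it through.** **Step 1. Is a cancelled patient already randomised?** Under Section 10.3.2, yes: allocation comes before registration is complete, so a registered patient has an arm. Under Section 5.3 taken alone, a cancellation could in principle fall between registration and randomisation. But Section 6.1.1 places both acts at Screening, so a patient found undosed at Visit 1 has been allocated under either order.

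**Step 2. Does another section protect that patient?** Section 6.6 covers those who stop taking the agent, which does not clearly include those who never took it. Section 5.11 does not address cancellation. No section states that all randomised patients are analysed. So nothing clearly keeps the patient in.

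**Step 3. Reproduce the plan's figures, to confirm the rates.** Inputs from Sections 9.2 and 9.3.1: control recurrence 35% at 12 months, competing events 20% at 12 months (10% transplant, 10% death), HR 0.45, 47 per group, two-sided alpha 0.1, 42-month accrual, 15-month follow-up, 10% drop-out, exponential times.
- Analytic sample: 0.80 × 0.90 = 0.72, and 130 × 0.72 = 93.6, stated as 94.
- Recurrence hazard: −ln(0.65)/12 = 0.0359 per month. Competing hazard: −ln(0.80)/12 = 0.0186 per month.
- These hazards with uniform accrual give 40.6 events. Power = Φ(√40.6 × |ln 0.45|/2 − 1.645) = Φ(0.899) = 0.816. Adding the drop-out gives 36.3 events and 0.777. The stated 80% lies between the two, so the rates are used as read.

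**Step 4. Patients exposed before first dose.** Expected number = 130 × (1 − exp(−hazard × days/30.44)).
- Transplant or death, 30 days: 130 × 0.0182 = 2.4, of which deaths (hazard −ln(0.90)/12) are about 1.1.
- Transplant or death, 15 days: 130 × 0.0091 = 1.2.
- Recurrence, 30 days: 130 × 0.0348 = 4.5. This counts recurrences arising, not documented.
- All three over one month: 1 − exp(−0.0545) = 5.3%, or 6.9 of 130.

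The 30-day figures assume that all 130 patients wait the full window. Section 4.5 allows study visits to be rescheduled for up to 2 months. If that applies to Visit 1 and the gap reached 60 days, transplant or death would be 130 × 0.0360 = 4.7.

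**Step 5. What a few lost events could do.** Take 65 per arm, no drug effect and 35% recurrence (22.75 events per arm). Removing k event patients from one arm only gives an apparent HR of ln(1 − (22.75 − k)/(65 − k))/ln(0.65):
- k = 1: 0.96
- k = 2: 0.93
- k = 3: 0.89

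For power, the documents state no event target. If all 65 per arm were followed to 12 months, 65 × (0.35 + 0.18) = 34.45 events give power 0.758. Losing 1 or 2 events lowers it to 0.747 or 0.735.

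**The case against.** The strongest reply is that the rule will rarely be used and will do little harm when it is.

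- **The trigger is not receiving therapy, not having an event.** A reader might infer that 5.3%, about 7 of 130, can be cancelled. The documents do not support that. Most of that count is recurrence, and Section 6.2.2 and the schedule list no imaging review at Visit 1; the first one after Screening is at Visit 2. Most recurrences arising in the gap would be undocumented when drug is dispensed, and the patient would be dosed. Section 6.7 also leaves continuation after recurrence to the investigator. This stands: the figure is an upper bound on events.
- **Thirty days is a maximum counted from Screening.** Central imaging review and eligibility verification must precede randomisation, and Section 6.1 allows screening procedures up to 60 days before registration. Actual randomisation may therefore fall after the Screening Visit and closer to Visit 1. This stands.
- **Cancelling a registration is not exclusion from analysis.** A reader might infer that the rule deletes events. Section 10.3 does not say so, and the biostatistician holds the master randomisation list. This stands as far as it goes: what can be shown is a permission to cancel, with no rule that keeps the patient.
- **Blinding.** Coordinators and investigators do not know the arm, so the one-sided removals in Step 5 are a worst case. This stands.
- **The completer restriction is the larger threat.** A patient who dies before first dose is already outside a month-12 completer analysis. True, but lifting that restriction would not recover a patient who was cancelled and never followed.
- **The criteria review at Visit 1.** The schema lists "review inclusion/exclusion criteria; interviewer-administered questionnaire; dispense study drug and diary" there, which might look like a second eligibility gate after allocation. The schema repeats the review at later visits, while Section 6.2.2 and the schedule do not list it at Visit 1, so it carries little weight.

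**Conclusion.** The point holds as a fault of wording with a real design consequence. Section 10.3 permits randomised patients to be lost after allocation, at discretion, and no section clearly retains them, although TTR, RFS and OS are counted from randomisation.

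The size is small. Transplant or death before first dose is at most about 2.4 of 130 over a full 30 days and about 1.2 over 15 days. Withdrawals, for which the documents give no rate, and the few recurrences documented before Visit 1 come on top. This rests on the plan's 12-month rates, constant hazards from randomisation, and every patient waiting the stated gap. A longer gap through rescheduling would raise the count. With blinded staff, material bias between arms is unlikely. The point is worth correcting because the rule is explicit and the remedy nearly free, not because it threatens the trial's result by itself.

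**What to change.** 1. In Section 10.3, limit the cancellation sentence to patients who have not yet been randomised.
2. Add there, and in Section 9.3.1, wording to this effect: *Every randomised participant, whether or not study agent is started, remains in the trial, is followed for all endpoints as in Section 6.6 (subject to consent), and is analysed in the assigned arm from the date of randomisation.* Extend Section 6.6 to name participants who never start.
3. Make the Study Summary's analysis-population sentence agree with this; as written, it would override item 2 for the primary objective.
4. Reconcile the order of registration and randomisation in Sections 5.3 and 10.3.2.

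This needs protocol wording only, with no added patients or visits; the follow-up concerns a handful of people. The statistical price is that a few never-treated patients stay in the analysis and slightly dilute the estimated effect.

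Randomising closer to Visit 1 would shorten the exposed gap, but it is optional. It would bring the email, RANDI3 and OnCore steps close to dispensing at five sites, and the correction does not depend on it.

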## 10.3.1 Eligibility Verification

Prior to registration, all subjects must undergo eligibility verification by the QMC at Cedars-Sinai. The following documents will be completed and provided for review:

- Registration form (or equivalent)
- Copy of required MedQIA CRF
- Full Eligibility Checklist (signed by a consenting investigator) with source
- Signed patient consent form and Subject's Bill of Rights
- HIPAA authorization form

Please see MOP for Eligibility Verification details.

